## 2.0 STUDY RATIONALE

This study adopts an alternative approach to immune therapy assessment by eschewing the treatment of late stage disease and evaluating adjuvant-based disease prevention in patients with minimal disease but at high risk for recurrence. According to the serial immune function analyses by Coleman (Coleman, Clayton et al. 2005), five of nine patients with Stages III-IV ovarian adenocarcinoma who achieved post-chemotherapy remission retained the capacity of CD8 $^{+}$  T-cell responses to a panel of 11 viral peptides restricted by at least six common HLA class I alleles. Chemotherapy produced no apparent effect on naïve (CD45RA $^{+}$ CCR7 $^{+}$ ), central memory (CD45RA $^{-}$ CCR7 $^{+}$ ), or effector memory (CD45 $^{-}$ CCR7 $^{+}$ ) T-cells. These findings affirm the strategy of vaccine deployment following chemotherapy, and justify selection of Stage III/IV epithelial ovarian cancer patients who have achieved complete clinical or pathological remission following cytoreductive surgery and front-line chemotherapy for this Vigil™ vaccine study. Exploratory analysis of two Phase III studies (D9901 and D9902) with the recently FDA approved Provenge® has identified prolonged

survival benefits in prostate cancer patients initially treated with Provenge® and subsequently received docetaxel (median survival of 34.5 months, compared to 25.4 months in patients treated with placebo followed by docetaxel) (Petrylak 2006). Thus the potential for vaccine mediated immune modulation both posterior and anterior to chemotherapy is a clinically attractive strategy worthy of exploration.

With regard to the appropriateness of a placebo arm in this group of patients, to date, in conjunction with platinum/taxol base regimens, maintenance therapies have shown neither a DFS endpoint advantage (Sabbatini, Harter et al. 2013) nor an OS (overall survival) endpoint advantage low dose taxol (Markman, Liu et al. 2009), Abagovomab (Sabbatini, Harter et al. 2013), and bevacizumab (Burger, Brady et al. 2011; Perren, Swart et al. 2011) while giving rise to a spectrum of extended treatment related side effects and questions of results-related economic justification (Lesnock, Farris et al. 2011). In the two recent randomized Phase III studies of bevacizumab, GOG-0218 (15 mg/kg x 16 cycles) and ICON7 (7.5 mg/kg x 12 cycles), in which there was a RFS endpoint advantage, the bevacizumab and control curves converged after discontinuation of bevacizumab prior to progression at 24 months and ~22 months, respectively, implying that continuation of bevacizumab until progression be considered, consistent with the results of the OCEANS trial in women with platinum-sensitive recurrent disease (for a significant RFS endpoint albeit there was still no significant difference in OS at first interim analysis) (Aghajanian, Blank et al. 2012). This must be weighed against the added exposure to bevacizumab associated adverse effects. As subsequently pointed out, the 3.8 month gain in PFS came at the patient cost of “23% risk for developing Grade 2 hypertension, 10% risk for Grades 3 to 4 hypertension, and 2.3% risk for Grade 3 or worse GI perforation, hemorrhage, or fistula formation”(Hensley 2011). In addition, based on Quality Adjusted Life Year (QALY), the cost of chemotherapy plus just 16 cycles of bevacizumab is \$326,530/QALY versus \$13,402/QALY for the same chemotherapy and maintenance low-dose paclitaxel (Lesnock, Farris et al. 2011). Likewise in a cost-effectiveness analysis of GOG-0218, the cost effectiveness ratio (i.e. the cost per year of PFS) was \$247,616, \$1,800,000 and \$5,500,000 for the paclitaxel (P) and carboplatin (C); P+C and bevacizumab (B); and P+C+B and maintenance B, respectively (Cohn, Kim et al. 2011). In the absence of a confirmed OS advantage, at least for front-line therapy for ovarian cancer, the additional cost is hard to justify (Hensley 2011; Tomao, Tomao et al. 2013); particularly so without FDA approval. Similarly Grade  $\geq 2$  toxic effects including peripheral neuropathy (15.5), infection/fever (19.9%), and dermatologic events (70.8%), are observed with maintenance therapy involving taxol (Mannel, Brady et al.). Despite a recurrence-free-interval delay in the SWOGS9761/GOG 178 study of 12 vs. 3 cycles of maintenance Taxol (22 vs. 14 months), long-term follow up revealed no survival advantage (53 vs. 48 months; p=0.34) (Markman, Liu et al. 2009). In addition, a Phase III study of maintenance Taxol x 6 cycles vs. observation revealed neither a progression-free survival nor overall survival advantage (Conte 2007). The attendant significant morbidity and lack of survival

benefit qualified the National Comprehensive Cancer Network (NCCN) commentary on use of Taxol maintenance as 2B with the further proviso recommending use in a clinical trial.

## 3.0 OBJECTIVES

### 3.1 Primary objective(s)

- To assess time to recurrence (TTR) following the administration of bi-shRNAfurin and GMCSF autologous tumor cell (Vigil™) vaccine.

### 3.2 Secondary objective(s)

- To identify and determine the effect of Vigil™ autologous tumor cell vaccine on immune surrogate markers in this group of patients.
- To assess the predictive potential of initial tumor infiltrating lymphocyte (TIL) and tumor associated macrophage (TAM) phenotypes.
- To enlarge the safety database of Vigil™ autologous tumor cell vaccine in patients with miminal disease.

## 4.0 STUDY DESIGN

### 4.1 Design

This is a Phase II open-label trial of maintenance Vigil™ autologous tumor cell vaccine. Tumor will be harvested at the time of surgical debulking (standard of medical care). Subsequently, patients achieving clinical CR following primary surgical debulking and doublet chemotherapy will be stratified for i) surgical stage (Stage IV or suboptimal debulking (>1 cm residual) Stage III disease versus Stage III patients with optimal debulking (<1 cm residual)) and ii) post-op chemotherapy, pre-vaccine CA-125  $>10 \leq 20$  U/mL versus  $0 \leq 10$  U/ml, then randomized 2:1 (Note: patients with Stage IIIC ovarian cancer will be additionally evaluated as a subset using descriptive statistics only). Patients will receive  $1.0 \times 10^7$  cells / intradermal injection of gene transfected autologous tumor cells, Vigil™, once a month for up to 12 doses as long as sufficient material is available. Enough harvested tissue to provide a minimum of 4 monthly injections will be required for entry into the study. These patients will be managed in an outpatient setting. Hematologic function, liver enzymes, renal function and electrolytes will be monitored monthly. Immune function analysis including

ELISPOT analysis of cytotoxic T cell function to autologous tumor antigens will be monitored at ( $\leq$ 24 hours before) tissue harvest,  $\leq$ 24 hours before the first cycle of chemotherapy (post debulking),  $\leq$ 24 hours before the third cycle of chemotherapy (post debulking), baseline (screening), prior to Vigil™ injection Months 2, 4, 6 and at EOT. The dates of the last dose of chemotherapy and the administration of Vigil™ vaccine #1 will be recorded.

Treatment will be continued until disease recurrence or exhaustion of the patient's vaccine supply. If  $\geq$  Grade 2 toxicity by NCI Common Toxicity Criteria (excluding Grade 2 fever  $\leq$  24 hours and Grade 2 and 3 injection site reactions) develops related to study treatment the vaccine dose will be reduced by 50% and continued on a monthly basis. If a single patient develops  $\geq$  Grade 3 toxicity (other than injection site reaction) related to study treatment the trial will be placed on hold for reevaluation of design in discussion with FDA. During this hold, no new subjects will initiate dosing, but subjects already being dosed may continue dosing as scheduled if deemed clinically appropriate by the PI.

## 5.0 STUDY POPULATION

### 5.1 Sample Size

Approximately fifty (50) treatment naïve patients with high risk Stage III/IV ovarian cancer who achieve clinical CR following surgical debulking and chemotherapy will be randomized in this trial.

### 5.2 Inclusion Criteria

Patients will be eligible for tissue procurement for the Vigil™ vaccine manufacturing process if they meet all of the following criteria:

1. Presumptive Stage III/IV papillary serous or endometrioid ovarian cancer.
2. Per Amendment #8, treatment naïve, high risk ovarian cancer will no longer be stratified, but the following information will be collected:
  - a. Stage IV or suboptimal ( $>1$  cm residual) Stage III disease versus Stage III patients with optimal ( $\leq 1$  cm residual) disease,
  - b. CA-125  $\leq 10$  U/ml versus CA-125 greater than 10 but less than or equal to 20 U/ml
  - c. IP chemotherapy versus IV chemotherapy
3. Availability of "golf-ball" size 10-30 grams tissue at time of primary surgical debulking.

4. ECOG performance status (PS) 0-2 prior to tumor debulking laparotomy.
5. Ability to understand and the willingness to sign a written informed consent document for tissue harvest.

Patients will be registered for inclusion in this study if they meet all of the following criteria:

1. Histologically confirmed Stage III/IV papillary serous or endometrioid ovarian cancer.
2. Clinically defined CR (no cancer related symptoms, normal physical examination and CT scan abdomen/pelvis and CXR, and CA-125  $\leq 20$  U/ml) following completion of primary surgical debulking. Patients enrolled must complete at least 5 but no more than 6 cycles platinum/taxane adjuvant or interval debulking + chemotherapy (or chemotherapy as per recommendations of NCCN guidelines, category 1 (IP chemotherapy included)). (Patients who complete surgery/chemotherapy with a CA-125  $> 20$  U/mL pre-registration have the option of being followed up to 2 months if serial CA-125 values continue to decrease at a rate of CA-125 decrease of  $\geq 50\%$  per month.)
3. Successful manufacturing of 4 vials of Vigil™ vaccine.
4. Recovered from all clinically relevant toxicities related to prior protocol specific therapies (including neuropathy to  $\leq$ Grade 2).
5. ECOG performance status (PS) 0-1.
6. Normal organ and marrow function as defined below:

Absolute granulocyte count	$\geq 1,500/\text{mm}^3$
Absolute lymphocyte count	$\geq 200/\text{mm}^3$
Platelets	$\geq 75,000/\text{mm}^3$
Total bilirubin	$\leq 2 \text{ mg/dL}$
AST(SGOT)/ALT(SGPT)	$\leq 2x$ institutional upper limit of normal
Creatinine	$< 1.5 \text{ mg/dL}$

7. Patients must be off all "statin" drugs for  $\geq 2$  weeks prior to initiation of therapy.
8. Ability to understand and the willingness to sign a written informed protocol specific consent document.

### 5.3 Exclusion Criteria

Patients will be excluded from this study if they meet any of the following criteria:

1. Surgery involving general anesthesia, radiotherapy, or immunotherapy within 4 weeks prior to randomization. Chemotherapy within 3 weeks prior to Vigil™ vaccine administration. Steroid therapy within 1 week prior to vaccine administration.
2. Patients must not have received any other investigational agents within 4 weeks prior to Vigil™ vaccine administration.
3. Patients with history of brain metastases.
4. Patients with compromised pulmonary disease.
5. Short term (<30 days) concurrent systemic steroids  $\leq$  0.25 mg/kg prednisone per day (maximum 7.5 mg/day) and bronchodilators (inhaled steroids) are permitted; patients requiring other steroid regimens and/or immunosuppressives at randomization are excluded.
6. Prior splenectomy.
7. Prior malignancy (excluding nonmelanoma carcinomas of the skin and carcinoma *in situ* cervix) unless in remission for  $\geq$  2 years.
8. Kaposi's Sarcoma.
9. Uncontrolled intercurrent illness including, but not limited to ongoing or active infection, symptomatic congestive heart failure, unstable angina pectoris, cardiac arrhythmia, or psychiatric illness/social situations that would limit compliance with study requirements.
10. Patients with known HIV.
11. Patients with chronic Hepatitis B and C infection.
12. Patients with uncontrolled autoimmune diseases.

#### **5.4 Withdrawal**

#### **Off Study Treatment**

Patients will be taken **off study treatment** if any of the following occur:

1. The patient experiences unacceptable ( $\geq$ Grade 3) toxicity felt to be related to treatment with the tumor cell vaccination that persists for  $>1$  week.
2. Persisting Grade 3 or 4 toxicity unrelated to treatment, defined as failing to normalize within 4 weeks.
3.  $\geq$  Grade 2 allergic reactions related to the study agent.
4. Grade 2 autoimmune reactions unless there is evidence of clinical benefit.
5.  $\geq$  Grade 3 autoimmune reactions.
6. An intercurrent illness, which would in the judgment of the investigator, affects assessments of clinical status to a significant degree or requires discontinuation of study treatment.

7. Non-protocol therapy (including, but not limited to, chemotherapy not listed as Level 1 Category of Evidence per NCCN Guidelines Version 3.2012, radiotherapy, hormonal therapy, immunotherapy, or surgery) is administered during study treatment.
8. Non-compliant with protocol or treatment.
9. Patient refuses to continue treatment.

The date of and reason for discontinuation must be noted in the Case Report Form (CRF). Every effort should be made to complete the appropriate assessments.

### **Stopping Rules**

Patients with disease recurrence will not receive further vaccine treatment. Withdrawal of patients from the study treatment will be in the event of unexpected and unacceptable vaccine-related toxicity,  $\geq$  Grade 2 allergic reactions, Grade 2 autoimmune reactions unless there is evidence of clinical benefit,  $\geq$  Grade 3 autoimmune reactions related to the study agent, or clinically significant disease progression.

## **6.0 INVESTIGATIONAL PLAN**

### **6.1 Patient Registration and Enrollment**

Written documentation of full, non-contingent IRB approval of the protocol and consent document must be on file before a patient can be registered. Patients will be assigned a tissue procurement number upon harvest and a vaccine number / patient number will be assigned upon completion of the manufacturing process.

Once eligibility has been confirmed, the site Research Nurse or Clinical Research Coordinator will email or fax the Registration Form and applicable de-identified records to [[contact]](mailto:[contact]) or [contact]. If sent by fax, and email should be sent to the above email address to alert the CRO of the incoming fax.

The received documents will be reviewed for completeness and sent to the Medical Monitor for review and randomization (if applicable). If records are not complete or if question arise, the site Research Nurse or Clinical Research Coordinator will be contacted for more information.

Please allow 48 hours for patient registration / randomization. Once confirmed, the completed Registration Form will be returned to the site indicating the assigned patient cohort.

## 6.2 Tumor Procurement

The investigative sites will ensure patients are scheduled for surgery for tumor procurement. Gradalis, Inc. will manufacture vaccine from the procured tissue, and thus will need to be notified at least 24 hours before the scheduled procurement in order to prepare for vaccine manufacturing (when possible). Additionally, tumors are to be procured on Mondays, Tuesdays, Wednesdays and Thursdays only due to the manufacturing being a 2-day process. Please contact the Sponsor if scheduling adjustments need to be made. Refer to the Tissue Procurement Study Reference Manual for instructions.

The equivalent of a “golf ball size” mass (10-30 gm tissue) and/or ascites fluid (preferably first paracentesis) is necessary for vaccine manufacturing. Radiological scans should confirm the presence of a lesion >3cm. If surgeons have the option of collecting more tissue, more doses of vaccine may be prepared (up to 12 doses). Vaccine manufacturing is rarely successful with small tumor masses. Lesions extending into bowel lumen cannot be processed.

Once the procured tissue is received at Gradalis, Inc. samples will be processed for autologous vaccine manufacture. No tissue or vaccine will be given to the participant or site apart from the outlined clinical protocol.

If available without compromising vaccine manufacture or pathology requirements, an aliquot of tumor will be collected for TIL and TAM immunophenotyping. Any excess tumor tissue, not used for vaccine manufacture will be used towards Vigil™ vaccine research and process development assays.

## 6.3 Vaccine Manufacturing

Gradalis, Inc. will manufacture vaccine from the procured patient tumors. Gradalis, Inc. will release vaccine once all release criteria have been met and eligibility has been confirmed.

## 6.4 Study Treatment Administration

Treatment will be administered on an outpatient basis. The site must contact the Mary Crowley CRO to obtain participant randomization assignment.

### **Recommended Chemotherapy**

Patients will receive 6 cycles of chemotherapy as either adjuvant or interval debulking + chemotherapy schedule. Recommended regimens are those classified as Level 1 Category of Evidence per NCCN Guidelines Version 3.2012. Regimens other than these should be discussed with the sponsor. Patients will not receive maintenance therapy other than that specified by protocol.

### **Vaccination Schedule and Dose**

Patients will be vaccinated according to the schedule outlined in Appendix B. Patients will receive Vigil™ vaccine at  $1 \times 10^7$  cells via intradermal injection for a minimum of 4 doses and a maximum of 12 doses starting  $\geq 3$  weeks following completion of chemotherapy (no longer than 2.5 months post chemotherapy).

Patients with viable cells in sufficient numbers (i.e. at least 4 doses of  $1.0 \times 10^7$  cells / injection) will receive monthly intradermal injections of the tumor cell vaccine for up to 12 months as long as sufficient material is available. Patients whose vaccine manufacturing fails to achieve a minimum of 4 doses will not undergo treatment.

### **Administration of Vigil™ vaccine**

The sites of injection will be rotated between the right and left upper arms. If the ipsilateral axillary lymph nodes were radiated or surgically removed during prior therapy, alternative sites (e.g., anterior thigh) will be used. The patient will be observed for at least 30 minutes (with a 10% window) following vaccination. During this observation period, vital signs will be taken every 10 minutes (with a 10% window). If clinically stable, vaccine administration may continue for up to 12 doses given on a monthly basis as long as sufficient material is available.

### **Vigil™ Vaccine Transfer**

All manufactured vaccine will be stored in the vapor phase of liquid nitrogen until ready for use. The site will contact Gradalis, Inc. when the study agent is needed for patient vaccine administration.

Gradalis will complete a Drug Transfer and Administration Form to release the patient vaccine. The clinic will sign off on the form upon receipt of the vaccination.

Please reference the Pharmacy Reference Manual for vaccine preparation and handling information.

### **Treatment Delay**

1. Treatment may be delayed no more than 4 weeks to allow recovery from toxicity.
2. Patients who delay treatment for more than 4 weeks due to toxicities will be considered off study treatment (see Section 4.4 Off Study Treatment).
3. Treatment delay not related to toxic events (including subjects unable to adhere to monthly injection) will not be delayed for more than three days. Unless a delay due to symptoms related to disease or infection in which case up to a 2 week delay is allowed.
4. If  $\geq$  one 2 week delay due to disease or infection occurs, patient status must be reviewed by sponsor.
5. If patients miss doses due to toxicities, the doses will be made up the following week and continue on a revised monthly schedule thereafter.

### **Dose Modification for Toxicity**

If  $\geq$  Grade 2 toxicity by NCI Common Toxicity Criteria (excluding Grades 2 and 3 injection site reactions) develops related to study treatment the vaccine dose will be reduced by 50% and continued on a monthly basis. If a single patient develops  $\geq$  Grade 3 toxicity (other than site reaction) related to study treatment the trial will be placed on hold for re-evaluation of design in discussion with FDA.

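### For vaccine-related allergic reactions and some autoimmune reactions, Section 5.4 stops the vaccine while Sections 4.1 and 6.4 continue it at half dose, and no text says which governs; 4.1 and 6.4 also disagree on short Grade 2 fever

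*Combined protocol and SAP*

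**What the plan says.** Section 6.4, Dose Modification for Toxicity, deals with vaccine-related toxicity of Grade 2 or higher: "excluding Grades 2 and 3 injection site reactions) develops related to study treatment the vaccine dose will be reduced by 50% and continued" monthly. Section 4.1 repeats the rule with a longer exception list. It opens with "excluding Grade 2 fever" (lasting 24 hours or less) and goes on: "Grade 2 and 3 injection site reactions) develops related to study treatment the vaccine dose will be reduced by 50% and continued". Neither section sets an upper grade, excepts allergic or autoimmune events, or mentions Section 5.4.

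Section 5.4, Off Study Treatment, is equally mandatory. Any one listed item takes the patient off vaccine. The relevant items are:

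- Item 1, Grade 3 or higher: "toxicity felt to be related to treatment with the tumor cell vaccination that persists for" more than one week.
- Item 3, at or above the stated grade: "Grade 2 allergic reactions related to the study agent".
- Item 4: "Grade 2 autoimmune reactions unless there is evidence of clinical benefit".
- Item 5, at or above the stated grade: "Grade 3 autoimmune reactions".

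The Stopping Rules paragraph in 5.4 repeats the allergic and autoimmune withdrawals.

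Three other places bear on the point. The synopsis (Duration) lets a patient with Grade 2 or higher toxicity continue with delayed or reduced doses if the PI thinks it best. Section 6.4, Treatment Delay item 2, refers to the off-treatment list as Section 4.4. Section 4.1 places the trial on hold after one related event of Grade 3 or above other than a site reaction, but adds that "subjects already being dosed may continue dosing as scheduled if deemed clinically appropriate by the PI".

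**The concern.** Two mandatory instructions cover some of the same events and give opposite actions. The action concerned is whether a patient who has had an allergic or autoimmune reaction to an autologous cell product is injected with it again. A site that follows 6.4 as written re-injects a patient whom 5.4 removes.

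The trial hold does not settle the matter. It is not triggered by Grade 2 events, and when it is triggered it leaves dosing of patients already on vaccine to the PI. Enlarging the safety database is a secondary objective, and inconsistent re-exposure after the same event would make those data harder to interpret.

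The fever difference is a simpler contradiction between two statements of one rule, and fever is an expected event in Section 11.3.

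**Working it through.** The plan states no figure on this point, so the check is a comparison of the rules followed by simple counting.

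**Step 1. Overlap of triggers.** Each event below is taken as judged vaccine-related. That condition matters because items 4 and 5 of the 5.4 list do not themselves require relatedness, whereas 4.1 and 6.4 do.

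| Event | Section 5.4 | Sections 4.1 and 6.4 | Result |
|---|---|---|---|
| Allergic reaction, Grade 2 or above | Stop | Half dose, monthly | Conflict |
| Grade 2 autoimmune reaction, no clinical benefit | Stop | Half dose, monthly | Conflict |
| Autoimmune reaction, Grade 3 or above | Stop | Half dose, monthly | Conflict |
| Grade 2 autoimmune reaction with clinical benefit | Not listed | Half dose, monthly | None |
| Other Grade 2 toxicity | Not listed | Half dose, monthly (4.1 exempts short fever) | None with 5.4 |
| Grade 3 or above, over within one week, neither allergic nor autoimmune nor a site reaction | Not listed | Half dose, monthly | None |
| Grade 3 or above, lasting more than one week, neither allergic nor autoimmune nor a site reaction | Stop | Half dose, monthly | Can be applied in sequence (Step 2) |

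**Step 2. Persistent Grade 3 or higher toxicity.** Section 6.6 spaces doses 28 days apart, plus or minus 3, so the next dose falls no earlier than day 28 - 3 = 25, counting the last dose as day 0. An event starting on day 0 passes the one-week limit on day 8, before a half dose is due. An event that resolves sooner leads to the half dose. An event starting late in the interval could meet the half-dose rule first and the stopping rule afterwards. In each case the rules can be followed in order. The allergic and autoimmune items have no duration condition, so this reading does not reconcile them.

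**Step 3. Search for a precedence rule.** I looked at every available section on toxicity, dosing, delay, withdrawal and follow-up. None ranks 5.4 against 4.1 and 6.4. The one pointer from the dosing section to the off-treatment list names Section 4.4; the table of contents shows only 4.1 under Section 4.

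**Step 4. Ceiling on the difference per patient.** Inputs are 4 to 12 doses made and 1.0 x 10^7 cells per dose (Section 6.4). After an event at dose k of n, the injections in dispute number n - k.

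- Event at dose 1 of 4: 4 - 1 = 3 injections.
- Event at dose 1 of 12: 12 - 1 = 11 injections.
- Half dose: 1.0 x 10^7 x 0.5 = 0.5 x 10^7 cells.
- Cells in dispute: 3 x 0.5 x 10^7 = 1.5 x 10^7, up to 11 x 0.5 x 10^7 = 5.5 x 10^7.
- Under 5.4: 0 injections and 0 cells.

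**Step 5. Short fever.** After a related Grade 2 fever of 24 hours or less, each later injection is 1.0 x 10^7 cells under 4.1 and 0.5 x 10^7 under 6.4.

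**The case against.** The strongest reply is that the intended order can be recovered. Section 5.4 is a specific list, its Stopping Rules repeat the allergic and autoimmune withdrawals, and a dose rule naturally governs patients still on treatment. Section 6.4 (Administration) and Section 9.2 make continuation permissive and conditional on clinical stability. Section 7.6 gives sites a route for protocol questions, with a telephone line for urgent safety matters, and the sponsor releases vaccine on a form. Much of this stands: 5.4 is probably meant to prevail, and unnoticed re-dosing is less likely than the bare text suggests. What remains is that sites must infer the order on a safety instruction, from dosing sections whose exceptions omit these events and whose pointer to the list is wrong.

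A reader might infer several stronger conclusions that the documents do not support:

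- *All related Grade 2 or higher events are in conflict.* Most are not on the 5.4 list, so only the dose rule applies to them.
- *Persistent Grade 3 or higher toxicity is in conflict too.* The rules can be applied in sequence.
- *The exemption of Grade 3 site reactions in 4.1 and 6.4 contradicts 5.4 item 1.* Not halving for a site reaction, yet stopping if Grade 3 toxicity persists beyond a week, is coherent.
- *Endpoint results are distorted.* Section 13.3 counts recurrence even after stopping for toxicity, so time to recurrence is defined identically either way. Section 13.4 counts withdrawal for adverse events as treatment failure, but that measure is not among the objectives or listed efficacy assessments. It also censors non-failures at last follow-up, so the length of a dosing course is not a failure time to compare.

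**Conclusion.** The point holds for three vaccine-related events: allergic reactions of Grade 2 or above, Grade 2 autoimmune reactions without clinical benefit, and autoimmune reactions of Grade 3 or above. For these, stopping and half-dose continuation are both mandatory and unranked. The 4.1 versus 6.4 difference on short Grade 2 fever is a separate, direct contradiction.

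The per-patient ceiling is 0 against 3 to 11 half-dose injections. It assumes an event at dose 1, one injection per manufactured dose, every later dose given and no recurrence; a later event leaves fewer. For fever the difference is twofold in cells per later injection.

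How often the overlap would occur is unknown. Section 1.10 reports two possibly related Grade 3 events, with 33 patients treated. They were abdominal pain and neutropenia, neither reported as allergic or autoimmune. Section 11.3 says no autoimmune disease had been seen in vaccination studies to date, and no allergic-reaction rate is given. This is a safety-wording defect that should be corrected; it does not bear on the primary analysis.

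**What to change.** Four changes of wording in the next amendment:

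1. Begin the dose-reduction sentence in Sections 4.1 and 6.4 with *Unless Section 5.4 requires discontinuation,*.
2. Make the synopsis Duration sentence subject to Section 5.4, keeping the PI's discretion in all other cases.
3. Put the 4.1 exemption for Grade 2 fever of 24 hours or less into 6.4.
4. In Section 6.4, Treatment Delay item 2, change Section 4.4 to Section 5.4.

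The 5.4 list itself needs no change for this purpose. The cost is text in the synopsis, 4.1 and 6.4, with no new visits or data.
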